## Statistical Analysis Plan

Sponsor:

Protocol number:

The primary efficacy analysis will be performed on the ITT population and on the PP population as supportive. The secondary efficacy analysis will be performed only on the ITT population. The safety analysis will be performed on the Safety population.

Patients violating the criteria defined above will be excluded from any analyses.

The assignment of patients to analysis populations will be summarized before the database lock in the Patient Validation Document. Final assignment of patients to analysis populations will be approved by the Sponsor study team.

The list of protocol deviations leading to the exclusion from the analysis populations is reported in the Protocol Deviation Handling Document (PDHD).

Non-protocol deviations (NOPDs) detected through SAS® programming are not protocol violations but they lead to exclusion from analysis populations; they are listed in the following Table 3-2:

**Table 3-2: List of non-protocol deviations**

Deviation code	Description	Exclusion from analysis population
NOPD1	Patient who was not randomized	PP/ITT/Safety
NOPD2	Randomized patient who did not have receive at least one dose of study treatment	PP/ITT/Safety

\* NOPDs = Non-protocol deviations

## 5. VARIABLES

### 5.1. EFFICACY VARIABLES

#### PRIMARY EFFICACY PARAMETERS

- Treatment's success rate: percentage of infants who have more than a 50% reduction in the average daily duration of cries after 28 treatment days.

#### SECONDARY EFFICACY PARAMETERS

- Number of cries from baseline to the end of study (after 28 days) and presence of infantile colic at the end of study (after 28 days).
- Number of regurgitation and vomit.
- Number of infections of the respiratory system, gastrointestinal system, urinary system or skin during the study period.
- Daily evacuative frequency.
- Daily consistency of the fecal mass, evaluated through Bristol stool scale.

	Statistical Analysis Plan
	Sponsor:
	Protocol number:

- Bifidobacterium BB-12® effect on gut microbiota, on the fecal production of peptides from innate immune system (Calprotectina,  $\beta$ -defensin 2, LL37) and on fecal short chain-fatty acids production (butyrate and propionate).

## 5.2. SAFETY VARIABLES

### Adverse Events

Adverse events are defined as the appearance of undesirable sign(s) (included laboratory abnormal values), symptom(s) or medical condition(s) temporarily associated to a drug.

An Adverse Event will be defined as a Serious Adverse Event if the event:

- results in death
- is life-threatening
- requires in-patient hospitalization or prolongation of existing hospitalization
- results in persistent or significant disability/incapacity

or

- is a congenital anomaly/birth defect

An event that compromises patient safety will be considered as a Serious Adverse Event.

### Physical examination

Physical examination is evaluated at each visit. The following locations will be analyzed, considering if the result was normal, abnormal or not evaluated: hairs/skin, lymph nodes, eyes, ears/nose/throat, breast, respiratory, cardiovascular, abdomen, urogenital, pelvic, rectal, musculoskeletal, neurologic, mental status.

### Anthropometric data

Anthropometric data are collected at Visits T0, T1 and T5: weight (g), length (cm), cranium measure (cm), weight (g) / length (cm).

## 6. DEFINITION AND GENERAL METHODOLOGY

### 6.1. GENERAL METHODOLOGY

All statistical tables, listings and figures will be produced using SAS® for Windows release 9.4 (64-bit) or later (SAS Institute Inc., Cary, NC, USA). Continuous data will be summarized by mean,

	Statistical Analysis Plan
	Sponsor:
	Protocol number:

standard deviation (SD), median, 1st and 3rd quartile, minimum and maximum. Categorical data will be presented by absolute and relative frequencies (n and %) or contingency tables.

Percentages will be computed considering patients with non-missing information, if not differently specified.

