	
A patient who came back for Visit T2 was considered as having received at least one dose of study treatment.
 
The primary efficacy analysis was performed on the ITT population, and on the PP population as supportive. The secondary efficacy analysis was performed on the ITT population only. The safety analysis was performed on the Safety population.
 
Primary variable
 
Mean daily crying duration is described for each week by means of descriptive statistics for continuous data and was calculated on non-missing values; observations with values equal to zero were included in the computation. Mean change from baseline (mean of Week 1) was computed for each week.
 
The treatment success rate was evaluated in terms of the reduction of crying duration, comparing mean daily duration of the last Week (from T4 to T5) with that of Week 1 (from T0 to T1). Success was defined as a reduction $\geq 50\%$. The proportion of patients with successful outcomes in the two groups is summarized using descriptive statistics for categorical data and analyzed by means of a Chi-Square test.

Date and version	English version 1.0, 4 December 2019 – based on Protocol version 3, 16 May 2016 (document in Italian language)

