### 3.6. SAMPLE SIZE

According to the results of a previous trial that looked at a probiotic's effect on infants with CI, it is estimated that when the sample size in each group is 33, the study will have 80% power to detect an absolute difference of 35% in the treatment success rate (15% in the Placebo group and 50% in the treatment group) with a 0,05 alpha level.

The number of infants that will be included in the study is 80, with a dropout rate expected for a maximum of 20%.

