#### HANDLING OF MISSING DATA/IMPUTATION RULES/CENSORING RULES

Not Applicable.

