#### HANDLING OF DROP-OUT PATIENTS

Not Applicable.

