### 6.5.1. Primary efficacy analysis

#### Treatment's success rate.

Duration of crying will be collected daily in the diary during the entire study period. The average daily duration will be defined as the mean duration of all cries recorded during the day in the “Evaluation of crying” section (i.e. sum of episodes’ duration/number of cries during the day).

Weekly mean will be defined as the mean of the calculated average daily durations during the selected week and will be described by means of descriptive statistics for continuous data. Mean changes from baseline (i.e. mean of the first Week) to the mean of the selected week will be computed as well.

Treatment success rate will be evaluated in terms of reduction of duration of cries, comparing mean weekly duration of the last Week (from T4 to T5) and mean weekly duration of Week 1 (from T0 to T1). A success will be defined as a reduction  $\geq 50\%$ .

The proportion of patients with a success in the two groups will be summarized by means of descriptive statistics for categorical data and analyzed by means of a Chi-Square test.

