### 6.5.2. Sensitivity analysis on primary endpoint

Not Applicable.

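### On the likeliest reading the ITT primary analysis is an observed-case analysis, and no planned analysis shows how far the result depends on the missing infants

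*SAP*

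**What the plan says.** - **Endpoint.** SAP 6.5.1 defines success by "comparing mean weekly duration of the last Week (from T4 to T5) and mean weekly duration of Week 1 (from T0 to T1"), with a reduction of at least 50%. The proportions are compared by a chi-square test. No denominator is given, and no minimum number of diary days.
- **Default denominator.** SAP 6.1: "Percentages will be computed considering patients with non-missing information, if not differently specified". The protocol synopsis (Statistical methods, Primary variable) says that mean crying duration "was calculated on non-missing values; observations with values equal to zero were included in the computation".
- **Missing outcomes.** Under SAP 6.1, the entries "HANDLING OF MISSING DATA/IMPUTATION RULES/CENSORING RULES" and "HANDLING OF DROP-OUT PATIENTS" both read Not Applicable. So does SAP 6.5.2, "Sensitivity analysis on primary endpoint". SAP 3.6 plans 80 infants "with a dropout rate expected for a maximum of 20" percent.
- **Analysis sets.** SAP 4 defines ITT as randomised and dosed at least once, and takes return at T2 as the test of having been dosed. Table 3-2 removes infants who fail that test from the PP, ITT and Safety sets. SAP 6.4 dates first administration at T1. The supportive PP set holds only completers without a significant violation.
- **Disposition.** SAP 6.2 reports discontinuations and reasons by arm.
- **Daily mean.** SAP 6.5.1 divides the summed episode "duration/number of cries during the day".

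**The concern.** An infant who returns at T2 and leaves before T4 belongs to the ITT set but has no primary outcome. With no rule for such infants and a general default of non-missing patients, the natural implementation drops them from the chi-square table. An infant who took the product after T1 but did not return at T2 is dropped earlier still, from every set. The result would carry the ITT label, while the only other planned analysis, PP, adds no infant with a missing outcome. A reader would learn how many infants left and why, but not whether the conclusion survives plausible outcomes for them.

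The daily mean raises a separate problem that needs no dropout. A day without crying gives zero divided by zero. The protocol counts zeros; the SAP does not say what happens. An infant with no crying on any recorded day of the last week could then be treated as missing instead of as a success.

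**Working it through.** **1. The plan's own figure.** Inputs from SAP 3.6: 15% vs 50%, alpha 0.05 (two-sided assumed), power 80%. The pooled formula is n0 = [1.960 √(2 × 0.325 × 0.675) + 0.842 √(0.15 × 0.85 + 0.50 × 0.50)]² / 0.35² = 26.9, so 27 per group. With continuity correction, n = (n0/4)[1 + √(1 + 4/(0.35 n0))]² = 32.4, so 33, as stated. The SAP does not say whether the planned test is corrected, so results below are uncorrected, with continuity-corrected values in brackets. The maximum loss is 0.20 × 80 = 16 infants; split equally, 32 per arm remain.

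**2. Type I error if loss is related to outcome.** Assumptions: 40 per arm, no true effect, 15% success in both arms, every lost infant a failure. Each infant is a success (p), a lost failure (d) or a retained failure (1 − p − d). The expected observed-case rate is p/(1 − d). Error rates are by exact enumeration.

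| Loss, arm A / arm B | False difference | Type I error | In favour of A | In favour of B |
|---|---|---|---|---|
| 20% / 20% | 0 | 5.1% (2.1%) | 2.55% (1.1%) | 2.55% (1.1%) |
| 20% / 5% | 0.15/0.80 − 0.15/0.95 = 3.0 points | 6.4% (3.0%) | 5.3% (2.6%) | 1.1% (0.4%) |
| 30% / 10% | 0.15/0.70 − 0.15/0.90 = 4.8 points | 8.1% (4.0%) | 7.4% (3.8%) | 0.7% (0.2%) |

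The 30%/10% case is 12 + 4 = 16 of 80, the planned maximum; 20%/5% is 8 + 2 = 10 of 80. Arm A may be either product. The splits are assumptions.

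**3. Dependence on 8 missing per arm.**

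| Data (BB-12 vs placebo) | p |
|---|---|
| Planned rates, observed cases: 16/32 vs 5/32 | 0.003 (0.008) |
| Missing = failure: 16/40 vs 5/40 | 0.005 (0.011) |
| 0 BB-12 and 3 placebo successes among the missing: 16/40 vs 8/40 | 0.051 (0.088) |
| Smaller effect, observed cases: 14/32 vs 5/32 | 0.014 (0.029) |
| 0 BB-12 and 1 placebo success: 14/40 vs 6/40 | 0.039 (0.071) |
| 0 BB-12 and 2 placebo successes: 14/40 vs 7/40 | 0.075 (0.127) |
| 1 success in each arm: 15/40 vs 6/40 | 0.022 (0.042) |

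**4. Cry-free weeks treated as missing.** If a share q of successes drops out of the table, the success rate becomes p(1 − q)/(1 − pq). The documents give no q; 10% to 40% is assumed.
- 50% vs 15%, q = 0.1 in both arms: 0.4737 − 0.1371 = 33.7 points instead of 35.
- 50% vs 15%, q = 0.4 in both arms: 0.3750 − 0.0957 = 27.9 points.
- 50% vs 15%, q = 0.1 on BB-12 and 0.4 on placebo: 0.4737 − 0.0957 = 37.8 points.
- 80% vs 45%, q = 0.4 in both arms: 0.7059 − 0.3293 = 37.7 points.

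**5. What missing = failure would do.** If loss is random, with no true effect at 15%:
- Loss 20%/5%: rates of 0.15 × 0.80 = 12% vs 0.15 × 0.95 = 14.25%; type I error 6.6% (2.2%).
- Loss 30%/10%: 10.5% vs 13.5%; 7.7% (2.5%).
- Observed-case on the same losses: 5.0% (1.9-2.0%).

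Exact power at the planned effect with 20% random loss in each arm: missing = failure, 12% vs 40% at 40 per arm, 84.0% (76.4%); observed-case, 15% vs 50% at 32 per arm, 87.5% (80.0%).

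**The case against.** **The denominator.** SAP 4 and 6.5 name the ITT population for the primary analysis, which could count as specifying the denominator differently. That reading is open, but no rule gives an infant without T4-T5 data an outcome, so the chi-square table would be undefined. Either reading needs a repair. A reader might also infer from the sample-size allowance for dropout that lost infants are not analysed. The allowance shows only that loss was expected, not how those infants are counted.

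**Size of the harm.** A reader might infer that the trial's type I error is inflated, or that BB-12 is favoured. The documents support neither. Inflation needs outcome-related loss that differs by arm, which double-blinding and an indistinguishable placebo make less likely. The arm with more loss, if either, is unknown. With continuity correction, which the 33 per group implies, total error stays below 5% in all three scenarios; only the tail favouring the arm with more loss exceeds 2.5% (2.6-3.8%). Under random loss the observed-case analysis holds its level. All of this stands and limits the weight of the point.

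**Information available.** The endpoint is binary, and the SAP reports counts, percentages and disposition, so a reader could approximate a missing = failure analysis by hand. This stands in part: what is absent is a commitment made in advance.

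**The T2 rule** is explicit, in both documents, and the same for both arms. Infants who never return supply no post-baseline diary. That explains the convenience of the rule, but does not make the set all randomised infants, or even all dosed infants.

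**Cry-free days.** The protocol includes zeros for this variable and the SAP does not expressly exclude them. Only an infant whose recorded last-week days are all cry-free would lose the outcome. Both points stand. A reader might also infer that this gap always works against the better product; step 4 shows that it can go either way.

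**Documents not seen.** The protocol available is a synopsis of an Italian original, and the Protocol Deviation Handling Document is not included.

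**Conclusion.** The point holds as a gap that should be fixed, not as evidence of a biased result. On the likeliest reading the primary analysis is observed-case under an ITT label. It leaves out randomised infants who do not return at T2, and nothing planned tests its dependence on missing infants.

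The size depends on assumptions that the documents do not settle: the amount of loss (only a 20% maximum is given), its split by arm, and its relation to outcome. In the scenarios shown, type I error moves from 5.1% to 6.4-8.1% uncorrected, or from 2.1% to 3.0-4.0% corrected. A result at the planned rates is fairly robust to 8 missing per arm. A result of 14/32 vs 5/32 is not: two placebo successes and no BB-12 success among the missing move p from 0.014 to 0.075 uncorrected.

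The cry-free gap is separate and smaller. At the planned rates, with equal removal, it would shrink the difference from 35 to between 33.7 and 27.9 points. At other rates, or with unequal removal, its direction is open.

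**What to change.** 1. In SAP 6.5.1, count a recorded day without crying as zero, in line with the protocol, and keep it distinct from a day with no diary entry.
2. State the primary denominator, including how a partly completed last week is handled. Stop using return at T2 as the test of having been dosed, so that every randomised infant is accounted for in at least one analysis of the primary endpoint.
3. Replace Not Applicable in SAP 6.5.2 with sensitivity analyses on all randomised infants: missing = failure, and a tipping-point analysis over the number of successes among the missing in each arm. Multiple imputation from the weekly diary means is an option. Missing = failure should not become the primary rule by default. If the database is already locked, report these analyses labelled post hoc.

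The cost is SAP wording and some programming on data already collected. The sensitivity results may be less favourable: missing = failure has somewhat lower power (84.0% against 87.5% uncorrected), and it carries its own error cost when random loss differs by arm (6.6-7.7% uncorrected in the scenarios above).

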#### DEFINITION OF BASELINE

The baseline period for the present study is defined as visit T0.

#### CODING OF THERAPIES AND MEDICAL TERMS

Clinical/surgical history and adverse events will be coded using MedDRA version 19.1 ITA; prior / concomitant medications will be coded using WHO Dictionary B2 Q4 2015.

#### MISSING OR PARTIAL DATES

Not Applicable.

#### HANDLING OF MISSING DATA/IMPUTATION RULES/CENSORING RULES

Not Applicable.

#### HANDLING OF DROP-OUT PATIENTS

Not Applicable.

#### MULITPLICITY ISSUES

Not Applicable.

### **6.2. STUDY PATIENTS**

#### **Patient Disposition**

A complete description of patient disposition will be provided on the enrolled patients overall and by treatment group. The number and percentage of patients entered at each visit, as well as the number of patients who completed and discontinued the study will be provided with the reasons for discontinuation. A complete description of the number of protocol violators and the number of patients per deviation will be summarized in the Patient Validation Document.

The numerosness of the analysis population will be described overall and by treatment group and the reason excluding the patient from any analysis population will be provided.

#### **Patient Baseline Characteristics**

Demographic and baseline characteristics will be summarized overall and by treatment group on the Intention To Treat population.

Demographic/diagnosis information includes:

- Sex

	Statistical Analysis Plan
	Sponsor:
	Protocol number:

- Age (days) at baseline will be computed in terms of days elapsed from birth date to informed consent date. When dates of parents' informed consent signatures are different, the latest date will be considered for the computation.
- Diagnosis of IC, according to Rome III criteria, for infants <= 4 months
- Type of childbirth (natural or caesarean)
- Gestational age (weeks) will be described by means of descriptive statistics for continuous data, while days will be only listed.
- Birth weight (g) will be described by means of descriptive statistics for continuous data, while its percentile will be only listed.
- APGAR 5 minutes score
- Positive family history of allergic diseases
- Exposure to second-hand tobacco smoke within the home environment
- Positive family history of functional gastrointestinal diseases
- Clinical/surgical history will be evaluated checking if the infant had any clinical/surgical relevant event in the past.

If the infant had a relevant event that could exclude him or her from the study, a category was required: ears/nose/throat, ophthalmic system, respiratory system, cardiovascular system, gastrointestinal system, hepatobiliary/pancreas, renal system, urogenital system, neurologic system, blood/lymphatic, endocrine/metabolic, musculoskeletal system, skin, psychiatric, other (allergies included). The frequency and proportion of patients who reported each category at least once will be summarized and presented by category, ATC Code Level 2 and Preferred Term. Patients could have more than one specification.

Other background characteristics will be evaluated at visit T0 and will include information about infant's parents:

- Number of terminated pregnancies of the mother
- Parents' smoking habit (if the father/the mother were smokers).

### 6.3. PRIOR AND CONCOMITANT MEDICATIONS

Prior / concomitant medications will be evaluated checking if the infant took any therapy in the past / during the study and will be presented by System Organ Class, Preferred Term and ongoing status on the Intention To Treat population and on the Safety population respectively

### 6.4. DRUG EXPOSURE AND TREATMENT COMPLIANCE

	Statistical Analysis Plan
	Sponsor:
	Protocol number:

Exposure will be computed as the time in days elapsed from the date of the first study drug administration (Visit T1) to the date of the last study drug administration (if applicable) or to the date of the day before Visit T5.

## 6.5. EFFICACY EVALUATION

Efficacy data will be summarized by treatment. Primary variables will be analyzed on the ITT and PP populations while secondary variables will be analyzed on the ITT population only.

### 6.5.1. Primary efficacy analysis

#### Treatment's success rate.

Duration of crying will be collected daily in the diary during the entire study period. The average daily duration will be defined as the mean duration of all cries recorded during the day in the “Evaluation of crying” section (i.e. sum of episodes’ duration/number of cries during the day).

Weekly mean will be defined as the mean of the calculated average daily durations during the selected week and will be described by means of descriptive statistics for continuous data. Mean changes from baseline (i.e. mean of the first Week) to the mean of the selected week will be computed as well.

Treatment success rate will be evaluated in terms of reduction of duration of cries, comparing mean weekly duration of the last Week (from T4 to T5) and mean weekly duration of Week 1 (from T0 to T1). A success will be defined as a reduction  $\geq 50\%$ .

The proportion of patients with a success in the two groups will be summarized by means of descriptive statistics for categorical data and analyzed by means of a Chi-Square test.

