Criteria for evaluation	
Primary efficacy variable
 
The primary efficacy variable was the proportion of successful treatments, defined as a 50% or greater reduction in the average daily duration of crying episodes after 28 days of treatment.
 
Secondary efficacy variables
 
 • Decrease from baseline in the number of crying episodes and in the persistence of colics at the end of the study (day 28) • Decrease in the number of regurgitation and vomiting episodes • Number of respiratory, gastrointestinal, cutaneous and urinary infections during the study • Number of bowel movements • Consistency of fecal mass using the Bristol scale • Effects of BB-12 on intestinal microbiota • Variations of the intestinal production of innate immunity peptides (calprotectin, β defensin type 2, LL37) and short-chain fatty acids (butyrate e propionate) 
Safety variables
 
Safety was assessed based on the results of physical exams and on the incidence of adverse events (AE).

Statistical methods	
The following analysis sets were defined:
 
 • Per Protocol Set (PP): all randomized patients who completed the study without any significant protocol violation. • Intention to Treat Set (ITT): all randomized patients who received at least one dose of study treatment. • Safety Set: all randomized patients who received at least one dose of study treatment. 
Patients were analyzed according to the treatment received.

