### 2.1. PRIMARY OBJECTIVE

The primary objective is to estimate the treatment's success rate, defined as the percentage of infants who have more than a 50% reduction in the average daily duration of cries after 28 treatment days from baseline.

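### SAP 6.5.1 judges primary success on minutes per cry, not crying time per day, and gives no rule for a day without cries

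*SAP*

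**What the plan says.** SAP 6.5.1 (Primary efficacy analysis) builds the primary variable in three steps.

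- **Daily value.** "The average daily duration will be defined as the mean duration of all cries recorded during the day". The bracketed formula divides the summed episode "duration/number of cries during the day".
- **Weekly value.** The unweighted mean of those daily values.
- **Success.** The last week (T4 to T5) is compared with Week 1 (T0 to T1). "A success will be defined as a reduction" of 50% or more, and the two proportions are compared by chi-square test.

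The SAP does not say what value a day without cries takes. Missing-data handling and drop-out handling (6.1) and sensitivity analysis of the primary endpoint (6.5.2) are all marked as not applicable. By default, percentages use only patients with data (6.1).

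The Protocol synopsis, under Criteria for evaluation, has success "defined as a 50% or greater reduction in the average daily duration of crying episodes after 28 days of treatment". Under Statistical methods, Primary variable, it says "Mean daily crying duration is described for each week" and adds that "observations with values equal to zero were included in the computation". It shows no division by the number of cries.

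The threshold also varies within the SAP. Section 2.1 counts "the percentage of infants who have more than a 50% reduction in the average daily duration of cries", and section 5.1 uses the same strict wording: "percentage of infants who have more than a 50% reduction in the average daily duration of cries after 28 treatment days". SAP 6.5.1 and the Protocol both accept exactly 50%.

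**The concern.** On days with crying, the SAP variable carries only the average length of a cry. Fewer cries of the same length earn nothing, and extra short cries lower the score. The primary result would then show whether single cries became shorter, not whether infants cry less per day.

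On days without crying, the formula is 0/0. Someone programming from the SAP must choose between skipping such days and coding them 0, and the two choices can give different success rates from the same diaries. At the extreme, an infant with no cries in the last week, the best possible response, is either a success or has no value and may leave the denominator.

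The secondary cry count does not cover the gap. SAP 6.5.3 divides the number of cries by the days that had cries, so a gain in cry-free days does not show there either.

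**Working it through.** **The plan's own figure.** SAP 3.6 gives 33 per group for 15% against 50% success, 80% power and alpha 0.05. With a mean proportion of 0.325, the two-sided formula gives [1.96 × √(2 × 0.325 × 0.675) + 0.8416 × √(0.15 × 0.85 + 0.50 × 0.50)]² / 0.35² = 26.9. The continuity correction gives (26.9/4) × [1 + √(1 + 4/(26.9 × 0.35))]² = 32.4, so 33. The figure reproduces, but it does not show which definition of crying duration lies behind the 15% and 50%.

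**Formulas.** For day d, let m be the crying minutes and c the number of cries.

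- Total measure: sum of m over the week / 7 (minutes per day).
- SAP measure: mean over days of m/c (minutes per cry). When c = 0 this is 0/0, so I ran it both ways: cry-free days skipped, and coded 0.
- Success: reduction of at least 50% from Week 1 to the last week.

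The diaries below are illustrative assumptions with the same pattern on each crying day.

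**Crying on all 7 days of both weeks**

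| Week 1, per day | Last week, per day | Total, min/day | SAP, min/cry | SAP result |
|---|---|---|---|---|
| 6 × 35 | 2 × 35 | 210 to 70 (−67%) | 35 to 35 (0%) | failure |
| 1 × 180 | 6 × 60 | 180 to 360 (+100%) | 180 to 60 (−67%) | success |
| 90 + 4 × 15 | 1 × 60 | 150 to 60 (−60%) | 30 to 60 (+100%) | failure |
| 120 + 60 | 120 + 60 + 3 × 10 | 180 to 210 (+17%) | 90 to 42 (−53%) | success |
| 8 × 25 | 4 × 12 | 200 to 48 (−76%) | 25 to 12 (−52%) | success |

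The first four rows are classed differently by the two measures, two in each direction. The last row shows that the measures can agree.

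**Cry-free days in the last week (Week 1 is 5 × 40 every day: 200 min/day, 40 min/cry)**

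| Last week | Total, min/day | SAP, days skipped | SAP, days coded 0 |
|---|---|---|---|
| 5 × 40 on 2 of 7 days | 400/7 = 57.1 (−71%) | 40 (0%), failure | 80/7 = 11.4 (−71%), success |
| 1 × 40 on 4 of 7 days | 160/7 = 22.9 (−89%) | 40 (0%), failure | 160/7 = 22.9 (−43%), failure |
| No cries | 0 (−100%) | undefined | 0 (−100%), success |

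In the first row the SAP 6.5.3 cry count stays at 5 per crying day in both weeks. In the second row a zero rule does not rescue the infant, because the fall from five cries to one is still ignored.

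**General threshold.** Let every day of Week 1 have crying, with cry length L1. Let the last week have k crying days with cry length L2. With zero coding, success requires (k/7) × (L2/L1) ≤ 0.5, that is L2/L1 ≤ 3.5/k.

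| Cry-free days in last week | k | L2/L1 at most | Shortening needed, coded 0 | Shortening needed, skipped |
|---|---|---|---|---|
| 0 | 7 | 0.500 | 50% | 50% |
| 1 | 6 | 0.583 | 42% | 50% |
| 2 | 5 | 0.700 | 30% | 50% |
| 3 | 4 | 0.875 | 12.5% | 50% |
| 4 | 3 | 1.167 | none | 50% |

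Beyond 4 cry-free days, zero coding still needs no shortening. Skipping needs 50% as long as one crying day remains.

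**Threshold wording.** 4 × 40 to 4 × 20 is exactly −50%: a success under SAP 6.5.1 and the Protocol, a failure under SAP 2.1 and 5.1.

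**The case against.** The strongest reply is that misclassification presupposes that total minutes per day is the intended endpoint. The endpoint phrase in the Protocol and in SAP 2.1 and 5.1 can be read per episode, SAP 6.5.1 prints an explicit formula, and SAP 6.5.3 uses the same convention for sleep and temper. It may therefore be a deliberate choice. The ambiguity stands: only a later English synopsis of Protocol version 3 is available, so an undeclared change is not shown. However, the synopsis's statistical text describes a daily crying duration and no per-cry ratio, so the two texts still need reconciling.

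Second, the Protocol's zero rule partly answers the cry-free days. It points to zero coding and, if carried into the SAP, would settle those cases. It is not in the SAP, does not itself turn 0/0 into a zero, and leaves the errors on crying days as they are.

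Third, no effect on the trial result is shown. That is right. The diaries are invented and some are extreme. In a blinded randomised comparison, a score computed alike in both arms does not by itself favour an arm when treatment has no effect on crying. The damage is to what the result means and possibly to sensitivity; no inflation of type I error is shown.

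Finally, the threshold wording matters only at exactly 50%, and the cry-count denominator in SAP 6.5.3 concerns a secondary variable. Both are side points.

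**Conclusion.** The concern holds and should be fixed before the primary analysis is relied on. Followed exactly, SAP 6.5.1 measures minutes per cry, which does not answer the Protocol's question about daily crying duration. Relative to total minutes per day, a 67% fall can count as a failure and a doubling as a success. The SAP also leaves cry-free days undefined. That choice alone can move the same infant from a 0% to a 71% reduction, or make a fully cry-free last week either unclassifiable or a success.

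The arithmetic needs no distributional assumption. The word misclassified rests on total daily crying time being the target. How many infants would be affected, the net direction of bias and the effect on power cannot be derived from the documents, and none is claimed.

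**What to change.** Amend the SAP with a dated, documented change made before unblinding. The synopsis is written in the past tense and dated December 2019, so this may no longer be possible; in that case label the revised analysis post hoc.

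1. In 6.5.1, define daily crying duration as the sum of episode durations that day. A completed cry-free diary day is 0; an unfilled day is missing.
2. Define the weekly mean as total minutes over completed days divided by the number of completed days. State the minimum number of completed days for a valid week (4 of 7 would be one assumption). State how an ITT infant without a valid last week is classed, for example as not a success. These two settings are for the trial team to choose, but they must be written down.
3. Define success as a reduction of at least 50% from Week 1 to the last week, and align 2.1 and 5.1.
4. Keep minutes per cry as descriptive only.
5. State in 1.1 whether the definition matches Protocol version 3.

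As side items, divide the cry count in 6.5.3 by completed diary days. Also reconcile SAP 1.1, which drops the reduction in number of cries because the eCRF lacks the information, with 6.5.1 and 6.5.3, which both use cry counts.

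Programming cost is low: the daily sum is already the SAP numerator, and the new definition no longer needs the cry count that 1.1 puts in doubt. The procedural cost is real, because it changes the primary variable of a final, sponsor-approved SAP. The data must also separate completed cry-free days from unfilled ones. The diary completeness check in SAP 3.7 is the place to confirm this, but the documents do not show that it is recorded day by day.
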